Objectives	
Primary Objective: To evaluate the impact of a gynecologic brachytherapy-specific educational consent video in patients receiving brachytherapy on patient reported satisfaction
 
Secondary Objectives: Evaluate the integration of the brachytherapy-specific consent video on patient treatment-related anxiety

Number of Subjects	80
Diagnosis and Main Inclusion Criteria	Any patient with gynecologic cancer who is deemed to require a brachytherapy procedure, and is willing to participate is eligible for inclusion.
Study Product(s), Dose, Route, Regimen	Gynecologic brachytherapy video consent.
Duration of administration	Prior to consent for the gynecologic brachytherapy procedure.
Reference therapy	None.
Statistical Methodology	1:1 block randomization between standard and enhanced video consent. To address the study hypotheses, we will use two-sample t-test to compare satisfaction score in two groups (patients provided with standard of care verbal consent (arm A) vs. enhanced online accessible brachytherapy educational video (Arm B)).

STUDY TABLE

	Consult	Pre-Informed consent	Intervention	Post Informed Consent	Post Brachytherapy
History (Medical/Oncology)	X				
Demographics	X				
Eligibility criteria	X				
Physical exam	X				
Vital Signs	X				
Height, weight	X				
Performance status	X				
TNM stage	X				
Tumor histology	X				
Use/type of systemic therapy	X				
Brachytherapy dose/volume information					X
Physician workflow data			X		
Informed Consent			A, B		
NCCN distress score	X			X	X
Brachytherapy-specific survey	X			X	X
Brachytherapy educational video			B		

Arm A: Standard consent process

Arm B: Video consent process

1.0 BACKGROUND AND RATIONALE

1.1 Background

High dose-rate brachytherapy is a highly technical and integral component of the definitive treatment of gynecologic cancers. Gynecologic brachytherapy requires a skillfully coordinated team approach with a focus on the patient experience¹.

Patients associate high-quality care with the ability to participate in decision making and obtain reliable information about their health and treatment ^{3,4}.

Provider explanation of these complex information processes can be overwhelming despite a well-documented informed consent ⁹. Prior work from our group explored enhanced patient consent material on gynecologic brachytherapy understanding and patient satisfaction and quality of life ([name]). We found that brachytherapy specific take home materials in supplement to a standard verbal consent process resulted in high patient treated related satisfaction (Rash D, [name], J. Prospective Evaluation of Patient Satisfaction Following the Use of Visual Brachytherapy-Specific Educational Materials for Cervical Cancer. *Brachytherapy*. 2016 Jan-Feb;15(1):65-70. doi: 10.1016/j.brachy.2015.09.007).

This study seeks to engage and educate the patient regarding the expected treatment trajectory using audiovisual mixed multimedia that comprehensively discusses the entire brachytherapy procedural process. We hypothesize there will be a significant improvement in all evaluable metrics in the cohort of patients receiving the brachytherapy video which would translate into improved quality of delivered care, patient understanding, increased treatment compliance, and enhancement in provider-patient communication.

1.2 Study Intervention

This study uses a gynecologic brachytherapy specific patient education video for the consent process in radiation oncology. All patients will meet with the radiation oncologist and have the standard of care procedure consent performed. Arm B (intervention arm) will have the access to view the brachytherapy educational video via the UCSD radiation learning center (<https://ucsd.radonlearningcenter.org/ucsdradonlearningcenter>) after the standard consent, study consent, and prior to the first brachytherapy procedure.

1.3 Rationale

Brachytherapy is a highly technical and integral component of the definitive treatment of gynecologic cancers [1]. To enhance provider communication and patient engagement, our study investigates a video consent on impact of patient treatment-related outcomes.

We will use a detailed brachytherapy video in addition to the standard brachytherapy verbal consent to evaluate patient-reported satisfaction and patient anxiety for gynecologic high-dose rate brachytherapy (a radiation procedure).

2.0 STUDY OBJECTIVES

2.1 Primary Objectives

To evaluate the impact of a gynecologic brachytherapy-specific educational video in patients receiving brachytherapy on patient reported satisfaction

2.2 Secondary Objectives

To evaluate the use of the brachytherapy-specific educational video on patient treatment-related anxiety

2.3 Exploratory Objectives

To evaluate the number of views and completeness of views of the brachytherapy video by the patients. To examine the patient radiation doses, treatment planning aspects, and normal tissue doses on brachytherapy completion.

2.4 Endpoints:

2.4.1 Primary:

Using the brachytherapy specific questionnaire, we will collect three patient reported time points for impact: baseline, after the consent process and before the first brachytherapy procedure (both arms have the standard consent at the consultation, and arm B will have access to the brachytherapy video online), and prior to the last brachytherapy procedure. For primary outcome we will examine satisfactory scores assessed by the brachytherapy-specific survey at two time points: baseline and following consent.

2.4.2 Secondary:

We will examine satisfactory scores at three patient reported time points: baseline, after the consent process and before the first brachytherapy procedure, and prior to the last brachytherapy procedure.

Using the NCCN distress scale, we will examine patient treatment-related anxiety at three patient reported time points: baseline, after the consent process and first brachytherapy procedure, and prior to the last brachytherapy procedure.

2.4.3 Exploratory:

The view number and completeness will be recorded from the UCSD radiation oncology learning website. The dose distribution of the target volume, normal tissue volumes and doses, and treatment planning goals will be explored.

3.0 PATIENT ELIGIBILITY

3.1 Inclusion Criteria

Subjects must meet all of the inclusion criteria to participate in this study.

1. Patient has the ability to understand and the willingness to sign a written informed consent.

2. Patient must be female, all races and ethnic groups are eligible.
3. Must be > 18 years of age, or have parental approval for inclusion.
4. Must carry a diagnosis of gynecologic malignancy.
5. Is deemed to require high-dose rate gynecologic brachytherapy procedure (intracavitary, hybrid intracavitary/interstitial, or interstitial).
6. Any prior external beam radiation therapy is allowed.
7. Any performance status is allowed.
8. Women of child-bearing potential and men with partners of child-bearing potential must agree to use adequate contraception (hormonal or barrier method of birth control; abstinence) prior to study entry, for the duration of study participation, and for # days following completion of therapy. Should a woman become pregnant or suspect she is pregnant while participating in this study, she should inform her treating physician immediately.
 - A woman of child-bearing potential is any female (regardless of sexual orientation, having undergone a tubal ligation, or remaining celibate by choice) who meets the following criteria:
 - Has not undergone a hysterectomy or bilateral oophorectomy; or
 - Has not been naturally postmenopausal for at least 12 consecutive months (i.e., has had menses at any time in the preceding 12 consecutive months)

3.2 Exclusion Criteria

Subjects meeting any of the exclusion criteria at baseline will be excluded from study participation.

1. Patient has had prior high-dose rate gynecologic brachytherapy at any point in the past.
2. Patient is a non English speaker
3. Patient is unable to watch the video
4. Patient declines consent to the study
5. Study-specific exclusion criteria.
6. Patient has a severe or uncontrolled medical disorder that would, in the investigator's opinion, impair ability to receive study treatment (i.e., uncontrolled diabetes, chronic renal disease, chronic pulmonary disease or active, uncontrolled infection, psychiatric illness/social situations that would limit compliance with study requirements).

4.0 TREATMENT PLAN

4.1 Study Design

1:1 randomized trial using blocked randomization based on chronologic arrival in clinic, a group of patients will be randomized to the standard of care verbal consent (Arm A), or the standard of care consent plus the online brachytherapy informed video (Arm B). There will be three time points for the collection: After the standard consent process as the baseline, following the standard only vs standard and educational video consent process prior to the first brachytherapy procedure, and prior to the last brachytherapy procedure. The patients in the brachytherapy video consent process will be watching this online via the [UCSD Radiation Oncology Learning Center Website](#)

<https://ucsd.radonlearningcenter.org/ucsdradonlearningcenter>. The patient will be given a specific log in to use, and we will be able to track the number of times the patient watches the video and the completion of the video view. The patient is allowed to watch the video as many times as desired.

4.2 Duration of Study Treatment

In the absence of treatment delays, the treatment will continue through the end of the completion of the necessary external beam radiation therapy treatments, or conclusion of all gynecologic brachytherapy procedures.

4.3 Duration of Follow Up

The study intervention will conclude after completion of the final brachytherapy implantation and prior to discharge from clinic.

Discontinuation from Study Participation

Patients may be removed from study participation for the following reasons (in addition to those listed for discontinuation of study treatment):

- The patient or legal representative withdraws consent;
- The patient is lost to follow-up;
- The patient dies;
- It is the decision of the investigator.

5.0 Measurement of Effect

5.1 Brachytherapy-specific outcomes

Primary outcome of this trial will be change in patient satisfaction scores (difference of baseline and following the video consent) as assessed by the brachytherapy-specific survey. Secondary outcomes will include patient treatment-related anxiety(NCCN distress score).

6.0 ADVERSE EVENTS

6.1 An adverse event (AE) is any untoward medical occurrence in a patient receiving study treatment and which does not necessarily have a causal relationship with this treatment. We do not anticipate AE on this video study. Gynecologic Brachytherapy Video Consent

7. Product description:

We developed a novel gynecologic brachytherapy-specific video. Due to clinical time constraints, it is often not feasible to comprehensively cover the full expanse of a brachytherapy

procedure with the patient; however, this is a crucial part of the treatment process. The video and associated multimedia educational materials will be used to enhance patient education and understanding, and provider-patient communication.

Video weblink: <https://chtapps-prod.ucdmc.ucdavis.edu/VideoConf/VCVideo/BRACHYSixthCut.mp4> will be posted to the [UCSD Radiation Oncology Learning Center Website](https://ucsd.radonlearningcenter.org/ucsdradonlearningcenter)
<https://ucsd.radonlearningcenter.org/ucsdradonlearningcenter>

Availability: Supplied by UCSD PI, [name].

How supplied: Audiovisual digital multimedia.

Storage and stability: On UCSD computing devices, behind institutional firewall, and subject to computing and technology requirements.

Route of administration for this study: Patient views video prior to gynecologic brachytherapy.

Side effects: There are no anticipated side effects.

8.0 SAMPLE SIZE AND STATISTICAL PLAN

This is a single site, randomized, open-label trial comparing the effect of the brachytherapy specific video versus verbal standard consent in patients receiving gynecologic brachytherapy(N=80).

8.1

Study Design/Study Endpoints

In this open-label study design, eligible participants will be randomized using a simple 1:1 schedule to either brachytherapy verbal standard consent (Arm A), or the brachytherapy specific video (Arm B), based on chronological arrival in clinic. There will be three time points for the collection: after the standard verbal consent process at baseline, following the standard vs video brachytherapy education, and prior to the last brachytherapy procedure.

Primary outcomes will be judged from a Likert-scale questionnaire. Patients will be given a Likert-scale questionnaire to assess their satisfaction with the information provided about the brachytherapy procedure which was adapted from a previously-published, validated instrument, and was published by our brachytherapy group². We will also assess the reduction in procedure-related anxiety based on the video intervention using the validated National Comprehensive Cancer Network patient anxiety screening tool.

8.2 Power and Sample Size Determination

Study Power: Estimates of study power are based on two-sample t-tests comparing outcomes between patients provided with brachytherapy informed video versus standard of care verbal consent. We based power estimates on a sample-size of 80 participants (40 pts with brachytherapy informed video and 40 with standard of care verbal consent). We used PASS 14 (NCSS Statistical Software). Assuming a two-sided test with alpha=0.05, we have 80% power to detect a 3.2 mean difference between armse.g., 57.5 mean score in patients with brachytherapy informed video versus a 54.3 mean score in patients with standard of care verbal consent, assuming SD of 2.7 and 6.4, respectively.

Accrual will be based on chronological arrival in clinic. Approximately 250 brachytherapy gynecologic procedures are performed at UCSD and collaborating sites annually. Accrual of 80 participants could occur over 2 years. Annual target accrual will be 40 participants per year.

8.3 Evaluable Subjects and Subject Replacement

The intent-to-treat (ITT) data set will include all eligible individuals who are randomized. The per-protocol (PP) data set will include all patients having completed all three data collection time points as assessed by the brachytherapy-specific survey, and NCCN distress score.

Data will not be analyzed until we have reached target accrual. Given the short duration of the intervention to the end of treatment we do not anticipate any issues with the number of evaluable subjects. Should a subject withdraw an additional subject would be randomized and enrolled. A slight imbalance is accepted.

8.4 Efficacy Analysis

8.4.1 Analysis of Primary Endpoint

The primary analysis will be based on the Intention-to-Treat population, defined as all individuals who were randomized to arm A or arm B. A Likert-scale questionnaire is used to calculate satisfaction score.

Using the brachytherapy specific questionnaire, we will examine three patient reported time points for impact: baseline, after the consent process, and prior to the last brachytherapy procedure. For primary endpoint, we will use a two-sample t-test to compare differences of satisfaction scores at two time points (baseline and following consent process) between groups. We do not anticipate any possible confounders, if any we will include it in the secondary analysis.

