8.4.2 Handling of missing data

In primary analysis, outcome values will not be imputed. Further sensitivity analysis for the impact of potential missing data will be conducted following study completion using multiple imputation analysis.

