8.4.3 Analysis of Secondary Endpoints

Satisfactory scores at three time points will be analyzed using a mixed effect model for repeated measures (MMRM) to assess satisfactory scores trajectories between two arms. The MMRM model will include terms for time, consent arm, baseline score, arm-by-time interaction, baseline score by time interaction, plus covariates that include age, stage. Time will be treated as categorical.

If values of last two time points are similar, analysis of covariance model (ANCOVA) will be used to model the change in satisfactory scores. The mean of the last two time points will be calculated. That is, the after consent score (mean values) will be regressed upon baseline score and consent arms. Patient treatment-related anxiety between groups, defined as NCCN distress score, are also collected at three time points and will be analyzed using the same strategy.

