Appendix C. Patient Reported Satisfaction

Appendix C: Treatment Specific Patient Reported Satisfaction

Question	Strongly disagree (1)	Disagree (2)	Uncertain (3)	Agree (4)	Strongly agree (5)
I am satisfied with:					
The information I have been given about my cancer treatment					
The information I have been given about possible side effects					
The information I have been given on what to do if side effects happen					
Explanations about possible interactions between my prescribed cancer treatments and other treatments I am thinking about using					
The way treatment information is presented to me, it is clear and easy to understand					
I get enough opportunity to ask questions about my cancer treatment					
I get enough opportunity to ask questions about how to manage side effects					
Available information resources such as handouts and staff					
The manner in which the information is provided. It is friendly, respectful, non judgmental					
To make informed choices about my cancer treatment					
To make informed choices about how to manage side effects

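### The 80% power is stated for a comparison of mean scores, but the deciding test is an unadjusted t-test on change from baseline; ANCOVA on the baseline already collected would be the better primary analysis

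*Combined protocol and SAP*

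**What the plan says.** Section 5.1 defines the primary outcome as "change in patient satisfaction scores (difference of baseline and following the video consent". Section 8.4.1 gives the matching test: "we will use a two-sample t-test to compare differences of satisfaction scores at two time points (baseline and following consent process) between groups". Baseline is not a covariate in that test.

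Section 8.2 sizes the trial on something else. Its example is a "57.5 mean score in patients with brachytherapy informed video versus a 54.3 mean score in patients with standard of care verbal consent". The SDs used are 2.7 for the video arm and 6.4 for the standard arm, with 40 patients per arm, two-sided alpha 0.05 and 80% power for a difference of 3.2. It does not name the visit at which those means and SDs apply.

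The Statistical Methodology row of the Study Summary says only "we will use two-sample t-test to compare satisfaction score in two groups" and does not mention change.

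Baseline adjustment appears only among the secondary analyses in 8.4.3. One is a repeated-measures model with baseline score as a term. The other is an ANCOVA, used only if the last two time points are similar, in which "the after consent score (mean values) will be regressed upon baseline score and consent arms". On missing surveys, 8.4.2 says "In primary analysis, outcome values will not be imputed".

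**The concern.** Values of 57.5 and 54.3 can only be score levels on this questionnaire, so the natural reading is that 2.7 and 6.4 are SDs of scores. The test that decides the trial uses a different variable. The SD of a change depends on the baseline SD, the follow-up SD and the correlation between them. The plan gives no baseline SD, no correlation and no SD of change.

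Validity is not at stake. Under randomisation the t-test on change is unbiased and holds its type I error. What is at stake is power and precision. If the correlation is modest and the baseline SD is large, subtracting the baseline adds noise, and the trial could be well short of 80%. A baseline-adjusted estimate will be produced anyway, but only as a secondary result that does not decide the trial.

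**Working it through.** **Inputs from section 8.2.** Difference d = 3.2; SD 2.7 (video, arm B) and 6.4 (standard, arm A); 40 per arm; two-sided alpha 0.05.

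**Assumed, because the plan is silent.** The two SDs and the 3.2 difference refer to the post-consent score. The baseline SD, s, is the same in both arms and lies between 2.7 and 6.4; the middle value is √((2.7² + 6.4²)/2) = 4.91. The baseline/post-consent correlation, r, runs from 0 to 0.7. Power is from the noncentral t with Welch degrees of freedom.

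**1. The plan's own figure.** For a comparison of scores:

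SE = √((2.7² + 6.4²)/40) = √(48.25/40) = 1.098; d/SE = 2.91; df = 52.5; power = 81.6%.

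The stated 80% is therefore reproduced for a test on scores.

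**2. What the change test needs.** Solving for 80% power at 40 per arm gives an SD of change of 5.04 if it is equal in the two arms. If it keeps the 6.4 : 2.7 ratio, the root mean square must be 5.01. The requirement is thus about 5.0 or less.

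**3. Change test.** The variance of change is s² + 6.4² − 2·r·s·6.4 in arm A and s² + 2.7² − 2·r·s·2.7 in arm B.

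Example, s = 6.4 and r = 0.5:
- Arm A: 40.96 + 40.96 − 40.96 = 40.96
- Arm B: 40.96 + 7.29 − 17.28 = 30.97
- Root mean square SD = √(71.93/2) = 6.00
- SE = √(71.93/40) = 1.341; d/SE = 2.39; power = 65%

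**4. ANCOVA of the post-consent score on arm and baseline.** The common slope is b = r(6.4 + 2.7)/(2s), so b·s = 4.55·r and s cancels. The residual variance in each arm is SD² + (b·s)² − 2·r·(b·s)·SD.

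Example, r = 0.5, b·s = 2.275:
- Arm A: 40.96 + 5.18 − 14.56 = 31.58
- Arm B: 7.29 + 5.18 − 6.14 = 6.32 (unrounded inputs)
- SE = √(37.90/40) = 0.973; d/SE = 3.29; power = 90%

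**5. Power at 40 per arm**

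| Analysis | r = 0 | r = 0.3 | r = 0.5 | r = 0.7 | r needed for 80% |
|---|---|---|---|---|---|
| Change test, s = 6.4 | 42% | 53% | 65% | 82% | 0.68 |
| Change test, s = 4.91 | 53% | 67% | 79% | 93% | 0.51 |
| Change test, s = 2.7 | 71% | 82% | 90% | 96% | 0.25 |
| ANCOVA, any common s | 82% | 85% | 90% | 96% | – |

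Simulated ANCOVA power with heteroscedasticity-robust (HC3) standard errors was 80/84/89/96% across the same correlations. In the simulations, rejection under the null was 4.6% to 4.9% for ANCOVA with HC3 and 4.9% to 5.2% for the change test.

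**6. Incomplete surveys.** Assume 10% of patients have no usable score, leaving 36 per arm. The score test falls to 77%. At r = 0.5 the change test falls to 61%, 75% and 86% for s = 6.4, 4.91 and 2.7. ANCOVA with HC3 gives 76/79/85/94% at r = 0/0.3/0.5/0.7, so it has no margin when the correlation is low.

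**7. A check on the inputs.** Appendix C as shown has 11 items scored 1 to 5, so the largest possible sum is 11 × 5 = 55. That is below the assumed mean of 57.5. The table may have been cut in extraction, but the scale behind the 8.2 inputs needs confirming.

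**The case against.** The strongest counter-argument is that a single low correlation for both arms is too pessimistic. Sections 4.1 and 8.1 place the baseline survey after the standard verbal consent. Arm A is offered no study video before the second survey, so its correlation may be close to test-retest. With s = 6.4 and r = 0.8 in arm A, the change test has 83% power if r is 0.5 in arm B and 77% if it is 0.3; with 0.9 and 0.5 it has 89%. This stands: the 53% and 65% cells are not predictions. It does not rescue the 80%, because 0.7 in arm A with 0.3 in arm B gives 71%. ANCOVA still gains in all these cases, reaching 93% to 99%. The same timing makes the favourable case of baseline SD 2.7 doubtful, since section 8.2 attaches SD 6.4 to patients with standard verbal consent.

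Other points stand in part:

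- Section 8.3 replaces patients who withdraw, so the 36-per-arm figures apply only to surveys missing for other reasons, at an assumed rate.
- HC3 is a reasonable choice, not a necessity. With 1:1 allocation, ordinary ANCOVA standard errors gave null rejection of 5.1% to 5.5% in simulation.
- The secondary repeated-measures model already adjusts for baseline. Moving adjustment into the primary analysis improves efficiency; it does not correct a bias.
- Normal theory may fit poorly near the top of a bounded scale, so the power figures are less certain than the mismatch between sections.

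**Conclusion.** The concern holds. The 80% in section 8.2 belongs to a comparison of scores (81.6% on recalculation), while sections 5.1 and 8.4.1 decide the trial on an unadjusted comparison of change. No input in the plan links the two. The figure is unsupported for the primary test but not refuted: at correlations 0.3 to 0.7 the change test has anything from 53% to 96% power, depending on the baseline SD.

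In every case calculated with model-based power, ANCOVA matched or beat the change test. The gain runs from 25 points (65% to 90% at baseline SD 6.4, correlation 0.5) to essentially nil (baseline SD 2.7, correlation 0.5 or more).

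These magnitudes assume that 2.7 and 6.4 are post-consent SDs, that 3.2 is the post-consent difference, that the arms share one baseline SD, and that normal theory is adequate. They are provisional until the visit and scale behind 8.2 are confirmed. If 2.7 and 6.4 were meant as SDs of change, the 81.6% would apply directly, and 8.2 should say so. This should be fixed; it does not invalidate the design.

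**What to change.** - **Sections 8.4.1 and 5.1, and the Study Summary:** make the primary analysis an ANCOVA of the post-consent satisfaction score on arm and baseline score, with HC3 standard errors in view of the unequal SDs assumed. Use one description of the primary variable throughout. With baseline as a covariate the estimated arm effect is the same for the score and for its change, so the change endpoint can keep its wording. Keep the unadjusted change t-test as a sensitivity analysis.
- **Section 8.2:** state that the 80% refers to a comparison of scores. Add that ANCOVA is expected to reach about that level or more if 2.7 and 6.4 are post-consent SDs and 40 per arm are analysed. Confirm the visit and the scoring range behind the means and SDs.
- **If the change t-test stays primary:** state and justify the assumed SD of change in 8.2 (about 5.0 or less is needed for 80%) and show power over a range of baseline SDs and correlations.

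The cost is a wording amendment that needs IRB approval before implementation (section 9.6). N = 80 is unchanged and no data or visits are added. HC3 costs about 1 point of power or less at correlations 0.5 and 0.7, and up to about 2 points at correlation 0. If the baseline SD is near 2.7, the change of method brings almost nothing, but it also loses almost nothing.
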